### 9.3. Analysis Set

For purposes of analysis, the following analysis sets are defined:

Participant Analysis Set	Description
Enrolled/Randomly assigned to study intervention	"Enrolled" means a participant's, or their legally authorized representative's, agreement to participate in a clinical study following completion of the informed consent process. Potential participants who are screened for the purpose of determining eligibility for the study, but do not participate in the study, are not considered enrolled.

Evaluable	All participants who are randomized, take at least 1 dose of study intervention and have baseline measurements and at least 1 post-baseline measurement.
Safety	All participants randomly assigned to study intervention and who take at least 1 dose of study intervention. Participants will be analyzed according to the treatment group they are randomized to unless the wrong study intervention is received throughout the study.

Defined Analysis Set	Description
FAS_Primary	In the evaluable analysis set, for participants who discontinue treatment, all post-discontinuation observations will be censored to missing.
FAS	In the evaluable analysis set, for participants who discontinue treatment, all observations post-discontinuation will be included in the analysis set.

## 9.4. Statistical Analyses

The SAP will be developed and finalized before any analyses are performed and will describe the analyses and procedures for accounting for missing, unused, and spurious data. This section is a summary of the planned statistical analyses of the primary and secondary endpoints.

### 9.4.1. General Considerations

The primary statistical method of MMRM will apply to continuous endpoints.

Statistical efficacy comparison will be made between each dose of vupanorsen and placebo for primary and secondary endpoints, respectively. Placebo-adjusted LS mean difference, 95% CI, and p-value will be presented. Since this study is exploratory in nature, no multiplicity adjustment of endpoints nor adjustment of multiple comparison to placebo will be made. Sensitivity analyses/supplementary analyses are defined in the SAP. Since the visit after Week 24 is considered safety follow-up, the statistical analyses at those visits will be presented but the p-value will be treated only as nominal.

In addition, a Bayesian  $E_{max}$  dose-response model will be estimated to illustrate the expected relationship between doses and their corresponding (percent) change from baseline at Week 24 for primary and key secondary endpoints, respectively. For each endpoint, 95% CI at each studied dose level will also be constructed.

If the baseline value is not available, the last measurement prior to the randomization visit will be used. However, for non-HDL-C and other lipid parameters, the baseline value will be calculated using the average of all values obtained at Screening and on Day 1 prior to dosing, except that for TG, when the initial value is exclusionary, the repeat value after the initial value and Day 1 value will be used to derive the baseline value.

In addition to analyses, summary statistics, listings, and figures will be provided.

#### **9.4.2. Primary Endpoint(s)**

The treatment effect of vupanorsen relative to placebo on the mean percent change/reduction from baseline in non-HDL-C at Week 24 will be estimated from the MMRM using the FAS\_Primary analysis set, ie, assuming all participants in the analysis maintain their randomized treatments. The LS-mean percent change from baseline at Week 24 along with 95% CI for each treatment group and placebo-adjusted LS-mean at Week 24 along with 95% CI and p-value for each vupanorsen treatment group will be presented.

A Bayesian  $E_{\max}$  dose-response model will be also be estimated using the FAS\_Primary analysis set, incorporating with the prior distribution of the  $E_{\max}$  model parameters estimated from the Phase 2a study. Sensitivity analyses will also be performed to evaluate the robustness of the primary analysis results (details are covered in the SAP).

#### **9.4.3. Secondary Endpoint(s)**

No multiplicity adjustments will be applied to secondary endpoints. All secondary endpoints will be primarily analyzed using the FAS\_Primary analysis set.

For continuous secondary endpoints, MMRM analyses will be implemented, with both LS-mean and placebo-adjusted LS-mean along with 95% CI, p-value at Weeks 4, 8, 12, 16, 20, and 24 estimated. The same type of Bayesian  $E_{\max}$  dose-response model will be estimated using the FAS\_Primary analysis set for each of the key secondary endpoints respectively. Sensitivity analyses will also only be performed on key secondary endpoints (details are covered in the SAP).

#### **9.4.4. Tertiary/Exploratory Endpoint(s)**

No multiplicity adjustments will be applied. All tertiary/exploratory endpoints will be analyzed using the FAS\_Primary analysis set.

For continuous tertiary/exploratory endpoints except for PK, MMRM analyses will be implemented, with both LS-mean and placebo-adjusted LS-mean along with 95% CI, p-value at Weeks 4, 8, 12, 16, and 24 estimated.

Listings of individual vupanorsen PK concentration values will be provided.

#### **9.4.5. Other Safety Analyse(s)**

All safety analyses will be performed on the safety population.

From the safety perspective, the following key laboratory endpoints will be explored:

- Change and percent change from baseline in HFF at Week 24
- Change from baseline in eGFR
- Change from baseline in ALT/AST
- Percent change from baseline in UACR
- Percent change from baseline in platelet counts
- Summary of ALT/AST abnormalities
- Summary of confirmed thrombocytopenia

TEAEs, SAEs, death, injection site reactions, ADA, ECGs, vital signs, immunogenicity, and other safety laboratory data, including categorical abnormalities in laboratory data, will be summarized/analyzed, listed, or presented in figures by treatment group or by treatment group and by visit where appropriate. All safety data, including data collected post the occurrence of intercurrent events, will be reported.

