Month	-1						1		2	3	4	5	6	8	
Visit Window (Days)					±1	±1	±2	±2	±2	±3	±3	±3	±3	±7	

- a. Day relative to start of study intervention (Day 1).
- b. Screening Period is a maximum of 28 days. Complete all inclusion/exclusion procedures and assessments denoted at Screening Visit 1; placebo injection training may be performed at Screening Visit 1 or Screening Visit 2. After participant has otherwise qualified for the study, including review of lipid and clinical laboratory results and completion of successful placebo training injections, perform MRI-PDFF at Screening Visit 3 or any time prior to randomization.
- c. If participants are not fasted for lipid panel and ApoB collection, perform other Screening activities and have participants return fasted for these tests.
- d. Screening Visit 1 activities should be completed within 7 days.
- e. Occurs 12 weeks after last dose: Week 32 for participants assigned to Q4W regimen or Week 34 for participants assigned to Q2W regimen.
- f. For participants who discontinue the study after Week 24, perform Follow-up procedures; do not perform Early Termination/Discontinuation procedures.
- g. For participants who discontinue study intervention or discontinue the study prior to Week 24, the procedures should be performed. Early Termination/Discontinuation procedures to be performed *as soon as practically possible* after decision to stop study intervention but participants should stay in study with continuation of scheduled visits unless participant withdraws consent from further study participation.
- h. Diary to be dispensed only to participants assigned to Q2W regimen.
- i. Laboratory results from Week 1 visit should be reviewed by the investigator prior to Week 2 dosing for participants dosing Q2W and prior to Week 4 dosing for participants dosing Q4W.
- j. Lipid panel and ApoB should be obtained with participants in a fasted state ([Section 5.3.2](#)). Lipid panel includes non-HDL-C, TG, direct LDL-C, total cholesterol, HDL-C, direct VLDL-C.
- k. Extended lipoprotein panel and FFA should be obtained with participants in a fasted state ([Section 5.3.2](#)). Extended lipoprotein panel includes Lp(a), ApoB-48, ApoB-100, ApoC-III, ApoA-I.
- l. ANGPTL3 should be obtained with participants in a fasted state ([Section 5.3.2](#) and [Section 8.6](#)).

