### 7.1.2. Discontinuation Criteria

In rare instances, it may be necessary for a participant to permanently discontinue study intervention (definitive discontinuation). Reasons for definitive discontinuation of study intervention include the following:

- Platelet count is  $<75,000 /\text{mm}^3$  on a re-test (ie, initial platelet count is  $<100,000 /\text{mm}^3$  and the repeat platelet count is  $<75,000 /\text{mm}^3$  or both the initial and re-test are  $<75,000 /\text{mm}^3$ ). Refer to [Appendix 10](#) for management of participants who discontinue due to decreased platelets as additional investigations must be conducted.
- The participant's eGFR falls to  $<15 \text{ mL}/\text{min}/1.73 \text{ m}^2$  and confirmed by a repeat laboratory measurement.
- Participant meets criteria for DILI (Hy's Law) as defined in [Appendix 6](#).
- AST or ALT elevations are  $>8 \times \text{ULN}$ , confirmed on a repeat laboratory measurement, regardless of total bilirubin or accompanying symptoms.
- A severe hypersensitivity reaction or severe injection site reaction occurs following a SC study intervention dose. Severe hypersensitivity reactions are defined as those causing anaphylaxis. Severe injection site reactions are defined as those in which ulceration or severe necrosis occurs.
- Participant becomes pregnant.

Note that discontinuation of study intervention does not represent withdrawal from the study. If study intervention is definitively discontinued, the participant will remain in the study to be evaluated during the regular visit schedule. See the [SoA](#) for data to be collected at the time of discontinuation of study intervention and follow-up for any further evaluations that need to be completed.

In the event of discontinuation of study intervention, it must be documented on the appropriate CRF/in the medical records whether the participant is discontinuing further receipt of study intervention or also from study procedures, posttreatment study follow-up, and/or future collection of additional information.

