## 9.1. Estimands and Statistical Hypotheses

### 9.1.1. Estimands

The primary estimand of this study will follow the hypothetical estimand approach to estimate the effect of treatment under the hypothetical condition that all participants maintained their randomized treatment through Week 24. This estimand is meant to estimate the pharmacological effect of the drug when taken as directed. It includes the following 4 attributes:

- Population: Participants with dyslipidemia taking a statin who meet the inclusion/exclusion criteria.
- Variable: The percent change from baseline in non-HDL-C at Week 24.
- Intercurrent event: All off-treatment data (ie, occurring at least 1 dosing interval after discontinuation of treatment), or data collected post treatment of severe hypertriglyceridemia (ie, change in statin dose or addition of TG lowering therapy; [Section 8.2.7](#)), if collected, will be excluded from analysis.
- Population-level summary: Difference of variable means between vupanorsen and placebo.

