#### 5.2. General Methods

##### 5.2.1. Analyses for Continuous Endpoints

Continuous endpoints will be summarized using the following descriptive statistics: number of subjects, arithmetic mean, standard deviation, median, minimum, maximum. Other descriptive statistics such as standard error, 1st quartile, 3rd quartile, IQR, etc. will

be added where appropriate. They will be summarized and tabulated by treatment groups and visits (including the 12-week safety follow-up visits when available), for the observed data and (percent) change from baseline.

For graphical summaries, mean +/- standard error, LS-Mean +/- standard error will be plotted for the observed data, (percent) change from baseline over time by treatment groups.

For statistical efficacy analyses, an MMRM model featuring the hypothetical estimand will be applied to primary and secondary endpoints, as primary analyses. All eligible post-baseline visits up to and including the analysis visit will be included in the MMRM model, in which baseline value, treatment (categorical), visit (categorical) and interaction term of treatment (categorical) by visit (categorical) will be treated as fixed effects and an unstructured covariance matrix will be used to account for the correlation among visits. If a model convergence issue is encountered with unstructured covariance matrix, then a simpler covariance structure, such as Toeplitz or compound symmetry will be considered. The restricted maximum likelihood (REML) method along with Kenward-Roger adjustment for degrees of freedom will be used for parameter estimation.

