### **6.3. Other Endpoint(s)**

#### **6.3.1. Safety Endpoints**

The following will be summarized according to [Section 5.2](#), using the safety analysis set defined in [Section 4.2](#).

- Incidence of treatment-emergent SAEs and AEs throughout the study.
- Incidence of AESI.
- Categorical summaries of clinical laboratory abnormalities:
  - ALT/AST abnormalities:
    - Value  $\geq 3$  x ULN;
    - Value  $\geq 5$  x ULN;
    - Value  $\geq 8$  x ULN.
  - Percent reduction from baseline in eGFR  $\geq 40\%$ .
  - Platelet abnormality:
    - Confirmed platelet counts  $< 100,000$ ;

- Confirmed platelet counts <75,000;
- Confirmed platelet counts <50,000.
- Platelet count changes:
  - Percent reduction from baseline in platelet counts  $\geq 30\%$ ;
  - Percent reduction from baseline in platelet counts  $\geq 50\%$ .
- UACR;
- ADA.

*Immunogenicity of vupanorsen will be assessed before, during, and after treatment. A listing of individual plasma ADA results (including ADA positive, negative, and unknown status samples and titers) sorted by treatment group, participant ID, planned visit, and the visit date/time will be reported. The incidence (number) and incidence rate (percent) of ADA positive, negative and unknown participants will be summarized by treatment group and planned visit and for the overall study. The ADA positive (ADA+) participants will be further subcategorized into TEADA if the baseline ADA is negative. The incidence and incidence rate of TEADA will be summarized by treatment group and planned visit and for the overall study.*

- ECG (Section 9.4.5.1. of the protocol);
- Vital signs (BP and pulse rate).

The following will be summarized and (percent) change from baseline will be analyzed according to [Section 5.2](#), using the safety analysis set:

- AST;
- ALT;
- Platelet counts;
- eGFR;
- Hepatic fat fraction;
- UACR.

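### By-visit mean changes in ALT, AST, platelets and eGFR include values after stopping drug, and no on-treatment version is planned, so later-visit means can understate the on-drug change.

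*Protocol*

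**What the plan says.** - **Data kept.** Protocol 9.4.5: "All safety analyses will be performed on the safety population". The same section ends: "All safety data, including data collected post the occurrence of intercurrent events, will be reported".
- **Analysis of change.** SAP 6.3.1 introduces a list that contains AST, ALT, platelet counts, eGFR, hepatic fat fraction and UACR with "The following will be summarized and (percent) change from baseline will be analyzed according to" Section 5.2, on the safety analysis set. It gives no window after the last dose. SAP Appendix 2.1 defines visit windows by study day only, and SAP Appendix 1 covers efficacy only.
- **Estimand.** SAP 5.2.1: "an MMRM model featuring the hypothetical estimand will be applied to primary and secondary endpoints, as primary analyses". No estimand is named for the safety laboratory endpoints. The summaries run by treatment group and visit, "including the 12-week safety follow-up visits when available".
- **Follow-up after stopping.** Protocol 7.1.2: after permanent discontinuation "the participant will remain in the study to be evaluated during the regular visit schedule". Footnote g of the Schedule of Activities: "participants should stay in study with continuation of scheduled visits unless participant withdraws consent from further study participation". Footnote o drops Day 169 PK, ECG, MRI-PDFF and banked samples for stoppers who completed the early termination procedures. Chemistry and hematology carry no such footnote.
- **Contrast with lipids.** The primary estimand in Protocol 9.1.1 excludes off-treatment data: "All off-treatment data (ie, occurring at least 1 dosing interval after discontinuation of treatment".

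**The concern.** A participant whose ALT, AST, platelets or eGFR meet a rule in Protocol 7.1.2 stops drug and keeps attending. From then on, that participant contributes a recovering value to the mean of the randomized arm. If more participants stop for laboratory reasons at higher doses, the later means of those arms are pulled further towards no change, and the dose gradient in mean change looks flatter than it was on drug.

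This matters because the protocol's own question is about a mean. Protocol 2.3.1 reports that rises in mean ALT appeared dose dependent in Phase 2a, and Protocol 4.3 says that small increases in mean ALT need study in a larger sample. Change from baseline in AST, ALT, platelets and eGFR is a listed safety endpoint, and the study is meant to support dose selection (Protocol 2.1). With 20 or 40 participants per arm, one person carries a weight of 1/20 or 1/40.

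**Working it through.** **1. The plan's own figure.** The documents give no figure for the laboratory means. The 15% discontinuation rate comes from Protocol 9.2, and its calculation reproduces: n = 20 × (1 − 0.15) = 17 per arm; half-width = 1.96 × 17.5 × √(2/17) = 11.76%; power for a difference of −20% is 91.5% by the normal approximation. This concerns non-HDL-C and is not affected.

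**2. Inputs.**
- From the documents: arms of 20 or 40; permanent stop on AST or ALT at a confirmed value above 8 × ULN, or on meeting the Hy's law criteria (Protocol 7.1.2); permanent discontinuation described as rare (same section); 15% discontinuation as a planning rate for all causes; terminal half-life of 3 to 5 weeks (Protocol 2.2.4.1).
- Assumed: change m = +0.2 × ULN in participants who stay on drug; on-drug change D = +7 × ULN in a stopper (from 1 to 8 × ULN), or D = +2 × ULN for someone who stops earlier for another reason; fraction f of D remaining at the later visit.

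**3. Arm mean ALT change at a visit after stopping.** With d the share stopped for the abnormality:
- all data: (1 − d)m + d·f·D
- off-drug values simply deleted: m
- stoppers counted at their last on-treatment value: (1 − d)m + d·D
- shortfall of the first against the third: d(1 − f)D

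| Arm, stoppers | D | f | All data | Deleted | Last on-treatment |
|---|---|---|---|---|---|
| 40, 1 | +7 | 0 | 0.975 × 0.2 = +0.195 | +0.200 | 0.195 + 0.175 = +0.370 |
| 40, 1 | +7 | 0.5 | 0.195 + 0.0875 = +0.283 | +0.200 | +0.370 |
| 40, 1 | +2 | 0 | +0.195 | +0.200 | 0.195 + 0.050 = +0.245 |
| 40, 2 | +7 | 0 | +0.190 | +0.200 | +0.540 |
| 20, 1 | +7 | 0 | +0.190 | +0.200 | +0.540 |
| 40, 6 (15%) | +7 | 0 | +0.170 | +0.200 | +1.220 |

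All entries are in × ULN. The last row treats the whole all-cause planning rate as ALT stops, so it is an extreme case. Temporary interruptions are left out.

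**4. Platelets and eGFR, one stopper in 40, full recovery.** With an assumed platelet fall of 67% in the stopper, the shortfall is 67/40 = 1.7 percentage points. With an assumed eGFR fall of 45 units, it is 45/40 = 1.1 units.

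**5. How complete recovery could be.** The drug remaining after t weeks at half-life h is 2^(−t/h). For h of 3 to 5 weeks this is 40% to 57% at 4 weeks, 16% to 33% at 8 weeks and 6% to 19% at 12 weeks. If laboratory values follow drug level, which is an assumption, recovery by Week 24 is near complete only after a stop at about Week 12 or earlier.

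**6. What an on-treatment MMRM would recover.** With two visits and dropout after the first, the estimate at the second is the stayers' mean plus slope × (earlier mean of everyone − earlier mean of stayers). In the first row of the table the earlier means are 0.370 and 0.200, a difference of 0.170. An assumed slope of 0.5 gives 0.200 + 0.085 = 0.285; a slope of 0.8 gives 0.200 + 0.136 = 0.336. Both lie between +0.195 (all data) and +0.370.

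**The case against.** Keeping all safety data is a sound choice, and the all-data mean is a fair answer to a treatment-policy question. It is low only as a measure of the on-drug change. The plan also does not rest on means. SAP 6.3.1 counts ALT/AST at 3, 5 and 8 × ULN, eGFR falls of at least 40%, and several platelet thresholds. SAP 6.6.2 adds shifts and listings. Protocol 8.3.8 makes ALT/AST, platelet or eGFR abnormalities that cause a missed dose or a stop adverse events of special interest, which covers the participants at issue. Visits up to and including the abnormal value count in full. All of this stands, but none of it gives an on-drug mean by dose.

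Four stronger readings are tempting, and the documents do not support them:
- **That harm is hidden, or the gradient is certain to be flattened.** The peaks are retained as above, stopping is expected to be rare, and the half-life slows recovery. The bias is conditional.
- **That best-case efficacy will be set against diluted safety.** SAP 2.1.3.1 and 5.2.1 plan treatment-policy analyses of non-HDL-C and the key secondary lipids on the FAS. The multiple-imputation one may be dropped (SAP 5.3), but the MMRM is unconditional. No section says that dose selection will compare laboratory means with FAS_primary lipid results, and SAP 5.1 plans no formal decision rules.
- **That UACR is affected in the same way.** It is neither a retest criterion (Protocol 7.1.1) nor a stopping criterion (7.1.2), so the mechanism is not shown for it.
- **That the sentence in Protocol 9.4.5 settles the matter alone.** It says that data are reported. Inclusion in the means follows from that sentence together with the safety set in SAP 6.3.1 and the lack of any window. Nor does the pointer to Section 5.2 clearly bring in the hypothetical estimand, which is tied there to primary and secondary endpoints.

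A last fair point is that a plain on-treatment mean is no cure. Deleting off-drug values removes the stoppers and gives +0.200 where the all-data mean is +0.195.

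**Conclusion.** The point holds as a conditional gap. For ALT, AST, platelets and eGFR, off-drug values enter the by-visit change analyses, the estimand is not stated, and no on-treatment version is planned. After laboratory-driven stops, later means can understate the on-drug change, more so in arms with more such stops.

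Under the assumed rise of 7 × ULN and full recovery, each stopper lowers the mean ALT change by 0.175 × ULN in an arm of 40 (7/40) and by 0.35 × ULN in an arm of 20 (7/20). With a rise of 2 × ULN the figures are 0.05 and 0.10, and half recovery halves them all. The documents fix neither the number of laboratory-driven stops nor the degree of recovery, so no single percentage understatement can be claimed. The primary analysis and sample size are untouched.

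**What to change.** In SAP 6.3.1, keep the all-data change analyses and leave the category tables, shifts and listings on all data. For ALT, AST, platelets and eGFR add:

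1. **An on-treatment MMRM by visit, with one explicit window after the last dose.** The FAS_primary label cannot simply be borrowed. Protocol 9.3 and SAP 4.1 remove every observation after discontinuation, while Protocol 9.1.1 and SAP 6.1.1.1 remove those at least one dosing interval later. One interval is also 2 weeks for Q2W and 4 weeks for Q4W, so such a window would cut follow-up differently in the regimen comparison that Protocol 4.3 wants. The value that triggered the stop should be in the model, because stopping on observed laboratory values is what makes missing-at-random plausible.
2. **Change to the last on-treatment value and to the worst post-baseline value, by arm.** These keep stoppers in the summary, which a raw on-treatment mean does not.

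State the estimand that each version targets: treatment policy for all data, hypothetical for the MMRM in (1), and while on treatment for the last on-treatment value; label the worst value as descriptive. Present the versions side by side. There is no need to rule that only the on-drug version may inform dose selection.

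The cost is SAP wording, a second set of tables, and a missing-at-random assumption in (1), which recovers only part of the gap. The worst value also tends to grow with the number of tests, including retests, so it should be read against placebo. No new data are needed.
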